#### *10.1.5.4.1 Final Visit - Visit 30 for study completers*

This visit will include:

- Record of concomitant medication
- Body weight measurement
- Physical examination including vital signs: SBP and DBP, heart rate
- Collect information on suspected efficacy endpoints
- Collection of cardiovascular events of interest other than efficacy endpoints (peripheral arterial disease, venous thromboembolic events)
- Collection of adverse events

- Data collection on IMP administration and IMP compliance check by review of diary and treatment kit accountability (used and unused kits)  
*NOTE: In case patient forgets to bring back diary at the visit, site should come up with an alternative solution to obtain as soon as possible information contained in patient diary in order to be able to complete final IMP information in eCRF.*
- Check of the compliance and stability of the dose of the LMT (atorvastatin, rosuvastatin, ± other LMT)
- 12-lead ECG
- Urinalysis (at selected sites), with urine sample sent to Central Lab
- Urine pregnancy test (females of childbearing potential only)
- Blood sample for:
  - Lipids: TC, LDL-C, HDL-C, TG, non-HDL-C, ApoB, ApoA-1, ratio ApoB/ApoA-1, and Lp (a)
  - Hematology: blood cell count including hematocrit, hemoglobin, red blood cell count, reticulocyte count, white blood cell count with differential count and platelets  
*NOTE: At selected sites with a longer transit time to Central Lab, a second hematology sample will be collected for local assessment of reticulocyte count*
  - Chemistry: glucose, sodium, potassium, chloride, bicarbonate, calcium, phosphorous, urea nitrogen, creatinine, uric acid, LDH, total protein, albumin, and  $\gamma$ GT
  - Liver panel (ALT, AST, ALP, and total bilirubin)
  - HbA1c
  - CPK
  - hs-CRP
  - Hepatitis C antibody test  
*NOTE: In case of positive hepatitis C antibody test at V30, patient should be recontacted as soon as possible after the site has been informed by Central Lab of this positive test, and a subsequent visit should be scheduled also as soon as possible, for collection of a confirmatory blood sample to be sent to Covance Central Lab.*
  - Library samples
  - Anti-alirocumab antibodies
- EQ-5D patient questionnaire
- IVRS/IWRS contact for notification of the date of this final visit; for patients still on treatment this will also be the end of treatment visit

This will be the final study visit for the patient. New or ongoing related or serious AE (as well as new or ongoing AESI) at this CSED visit should continue to be followed until resolution, stabilization, or death (whichever comes first) and related data will be collected (see [Section 6.2.1](#)).

#### 10.1.5.4.2 Final Visit - Visit 30 for prematurely discontinued patients

This visit will include:

- Collection of information on suspected efficacy endpoints
- Collection of cardiovascular events of interest other than efficacy endpoints (peripheral arterial disease, venous thromboembolic events)
- Collection of related and/or serious AEs
- Selected concomitant medications (statin, ezetimibe)
- Blood sample for
  - Lipids: TC, LDL-C, HDL-C, TG, non-HDL-C, ApoB
  - HbA1c
  - Anti-alirocumab antibodies
- IVRS/IWRS contact for notification of the date of this final visit

## 10.2 DEFINITION OF SOURCE DATA

Evaluations that are reported in the eCRF must be supported by appropriately signed identified source documentation related but not limited to the following:

- Agreement, date, and signature of informed consent mentioning the study identification
- Patient identification, last participation in a clinical trial, medical history, associated diseases, and data related to the studied pathology
- Contraception methods for women of childbearing potential
- Previous and concomitant medication (including the lipid modifying therapy)
- Study identification
- Treatment number, dates of administration
- Dates of visits and assessments including the examination report
- Vital signs, height, body weigh.
- Faxed central lab reports (dated and signed by the Principal Investigator or Sub-Investigator)
- IVRS/IWRS confirmation fax (screening, screen failure, training kit allocation, randomization, treatment reallocation, discontinuation, end of double blind treatment period, end of study, unblinding if applicable)
- ECG records signed and dated

- Adverse events and follow-up
  - In case of SAE, the site should file in the source document at least copies of the hospitalization reports and any relevant examination reports documenting the follow up of the SAE
- Date of premature study discontinuation (if any) and reason

Source documentation may be found in the following:

- Patient's identity
- Medical history
- Hospital records
- Nursing notes
- Physician's notes

### **10.3 HANDLING OF PATIENT TEMPORARY OR PERMANENT TREATMENT DISCONTINUATION AND OF PATIENT STUDY DISCONTINUATION**

All randomized patients should be treated with blinded study treatment (IMP) for as long as possible.

As a general rule, any IMP treatment discontinuation should be initially considered temporary, and Investigator should make best effort to resume IMP treatment as early as practically possible, after several weeks or months (pending there are no safety concerns), and perform all study visits and assessments as usual.

Permanent IMP discontinuation should be a last resort. Any IMP discontinuation should be fully documented in the eCRF and source notes.

Pregnancy will lead to permanent treatment discontinuation in all cases.

All randomized patients should be followed-up (and suspected efficacy endpoints collected) until the end of the study (common study end date visit), even if treatment was permanently discontinued early.

#### **10.3.1 Temporary treatment discontinuation with investigational medicinal product(s)**

Temporary treatment discontinuation (also referred to as treatment interruption) may be considered by the Investigator in case of AEs/SAEs or for other reasons. In general, every effort should be made to resume treatment with blinded study drug (IMP) following a temporary interruption. In case of AEs/SAEs, resuming treatment with the IMP will be done under close and appropriate clinical and/or laboratory monitoring once the Investigator has considered according to his/her best medical judgment that the responsibility of the IMP in the occurrence of the concerned event was unlikely and patient does not meet any permanent discontinuation criteria.

All treatment interruption duration should be recorded by the Investigator in the appropriate eCRF screens when considered as confirmed.

Treatment interruption is defined as one or more scheduled injections that are not administered to the patient, and typically as decided by the Investigator.

### **10.3.2 Permanent treatment discontinuation with investigational medicinal product(s)**

Permanent treatment discontinuation (also referred to as treatment discontinuation) is any treatment discontinuation associated with the definitive decision from the Investigator or the patient not to re-expose the patient to the IMP at any time.

Investigator is strongly encouraged to discuss with monitoring team before considering any treatment discontinuation as permanent. A discussion with National Coordinator may occur regarding other possible options.

### **10.3.3 List of criteria for permanent treatment discontinuation**

The patients may withdraw from treatment with the IMP if they decide to do so, at any time and irrespective of the reason, or this may be the Investigator's decision. All efforts should be made to document the reasons for treatment discontinuation and this should be documented in the eCRF.

Patients should discontinue the Investigational Medicinal Product (IMP) for the following reasons:

- Pregnancy, intention for pregnancy, or no longer with effective contraceptive method of birth control (females only)
- Acute injection reaction of clinical concern
- Serious adverse event (or non-serious but severe in intensity) of hypersensitivity reaction considered related to IMP
- At patient request
- If, in the Investigator's opinion, continuation with the administration of the IMP would be detrimental to the patient's safety or well-being (NOTE: please refer to [Section 10.4.7](#), [Appendix C](#) and [Appendix D](#), for management and follow-up of selected laboratory abnormalities, including guidance for treatment discontinuation)
- At the specific request of the Sponsor
- Any code breaking requested by the Investigator
- Patient receives double-blind treatment prior to randomization

Patient withdrawal from the study treatment or study should be avoided as much as possible. If this occurs, every attempt should be made to restart study drug if medically appropriate, whatever the duration of discontinuation. In case of permanent study treatment discontinuation, the appropriate follow-up until the common study end date visit should still be continued.

All efforts should be made to document the reasons for treatment discontinuation and this should be documented in the eCRF.

### 10.3.4 Handling of patients after permanent treatment discontinuation

Patients in whom IMP treatment discontinuation is considered permanent by Investigator should come for an extra visit (early end-of-treatment visit V70) as soon as practically possible (within 1 month) after IMP discontinuation is considered permanent by Investigator. V70 is similar to the common end of study visit (Visit 30, Month 64) for study treatment completers, and should include similar procedures.

Such patients must continue to remain in the study and will be strongly encouraged to complete all the remaining study visits as originally scheduled in [Section 1.2](#), until the common study end-date visit. Therefore, a contact should be maintained with these patients every 2 to 3 months (as per study assessments), and a clinic visit performed every 4 to 6 months until the common study end-date visit (V30).

- Over the 6 months following V70, all assessments (other than IMP administration and its associated procedures) should be performed as originally planned. These include but are not limited to collection of suspected efficacy endpoints, AE/AESI/SAE, concomitant medications, hematology and chemistry labs, lipid labs and anti- alirocumab antibodies.
- From 6 months post V70 until common study end date visit (V30), assessment at visits are simplified and will include updating patient contact information (as well as patients' family and patient's GP/cardiologist) and the collection of:
  - suspected efficacy endpoints
  - cardiovascular events of interest other than efficacy endpoints (peripheral arterial disease and venous thromboembolic events)
  - related and/or serious AEs
  - selected concomitant medications (statins, ezetimibe)
  - selected labs:
    - anti alirocumab antibodies, lipid panel and HbA1c: annually (at M12, M24, M36, M48, M60) and at common study end-date
    - ApoB at month 24 and at common study end-date.

Previously observed AEs/AESIs/SAEs that had not resolved should be followed-up until an outcome (e.g. resolution, stabilization) has been determined.

- In case of difficulty to comply with the 4 to 6-month clinic visit periodicity in patients who discontinued treatment early, every effort should be made to have an actual clinic visit at least annually (with periodic phone/internet contacts every 3 months in between) and a final visit V30. During that annual visit and at V30, selected blood samples as described above should be collected.

In rare cases of written withdrawal of consent (WOC) for follow-up visits (i.e. patient does not wish to come back even for an annual visit), and unless otherwise stated by the patient in the informed consent form, Investigators will be encouraged to get information from the general practitioner, any other physician, or other medical-care provider, in order to follow the medical status of the patients (especially when they withdraw their consent after having experienced an AE/SAE or a cardiovascular event [efficacy endpoint]). Investigators will also be expected to try as much as possible to re-contact those patients at the end of the trial, in order to obtain at least

their vital status (dead or alive), as well as their cardiovascular status if possible, and thus avoid lost to follow-up for the efficacy assessment.

If the patient exercises his right of opposition to transmission of the data to the sponsor or removal of data from the database, the investigator will inform, in writing, the clinical trial sponsor, and the sponsor will decide how to handle the subject data and samples based on local regulations and data privacy requirements.

All definitive discontinuation of study treatment should be recorded by the Investigator in the appropriate screens of the eCRF and in the patient's medical records when considered as confirmed. IVRS/IWRS should be notified when a patient prematurely discontinues study treatment.

### **10.3.5 Procedure and consequence for patient withdrawal from study**

The patients may withdraw from the study, before study completion if they decide to do so, at any time and irrespective of the reason or this may be the Investigator's decision:

- All study withdrawals should be recorded by the Investigator in the appropriate screens of the eCRF and in the patient's medical records when considered as confirmed (at least date of withdrawal and reason for). IVRS/IWRS should be notified when a patient prematurely discontinues study
- The patients should be assessed using the procedure normally planned for the visit V70 which corresponds to the early end of treatment visit. (see [Section 10.3.4](#))

However, all randomized patients should be followed-up (and suspected efficacy endpoints as well as related and/or serious AEs collected) until the end of the study (common study end date visit), even if treatment was permanently discontinued early.

In case of study treatment discontinuation (temporary or permanent) due to an adverse event, such patients will be closely monitored until the resolution or stabilization of this adverse event. This may mean that follow-up will continue after the patients have completed the study.

For patients who fail to return to the site, the Investigator should make the best effort to re-contact the patient (eg, contacting patient's family or private physician, review available registries or health care database), and to determine his/her health status, including at least his/her vital status dead or alive at minimum, preferably also stroke or MI status). Attempts to contact such patients must be documented in the patient's records (e.g., times and dates of attempted telephone contact, receipt for sending a registered letter). This will be clearly stated in the informed consent form.

For patients considered lost to follow-up, the eCRF must be completed up to the last visit performed. The statistical analysis plan will provide the details concerning the analysis of these patients.

Patients who have withdrawn from the study cannot be re-randomized (treated) in the study. Their inclusion and treatment number must not be reused.

## 10.4 OBLIGATION OF THE INVESTIGATOR REGARDING SAFETY REPORTING

### 10.4.1 Definitions of adverse events

Please refer to [Appendix E](#) for Adverse Event (AE) reporting requirements.

#### 10.4.1.1 Adverse event

An **adverse event** (AE) is any untoward medical occurrence in a patient or clinical investigation patient administered a pharmaceutical product and which does not necessarily have to have a causal relationship with this treatment.

#### 10.4.1.2 Serious adverse event

A **serious adverse event** (SAE) is any untoward medical occurrence that at any dose:

- Results in death, or
- Is life-threatening, or  
Note: The term “life-threatening” in the definition of “serious” refers to an event in which the patient was at risk of death at the time of the event; it does not refer to an event which hypothetically might have caused death if it were more severe
- Requires inpatient hospitalization or prolongation of existing hospitalization, or
- Results in persistent or significant disability/incapacity, or
- Is a congenital anomaly/birth defect
- Is a medically important event  
Medical and scientific judgment should be exercised in deciding whether expedited reporting is appropriate in other situations, such as important medical events that may not be immediately life-threatening or result in death or hospitalization but may jeopardize the patient or may require intervention (ie, specific measures or corrective treatment) to prevent one of the other outcomes listed in the definition above

**NOTE:** The following list of medically important events is intended to serve as a guideline for determining which condition has to be considered as a medically important event. The list is not intended to be exhaustive:

- Intensive treatment in an emergency room or at home for:
  - Allergic bronchospasm
  - Blood dyscrasias (ie, agranulocytosis, aplastic anemia, bone marrow aplasia, myelodysplasia, pancytopenia, etc)
  - Convulsions (seizures, epilepsy, epileptic fit, absence, etc)
- Development of drug dependency or drug abuse
- ALT >3 x ULN + total bilirubin >2 x ULN or asymptomatic ALT increase >10 x ULN
- Suicide attempt or any event suggestive of suicidality

- Syncope, loss of consciousness (except if documented as a consequence of blood sampling)
- Bullous cutaneous eruptions
- Cancers diagnosed during the study or aggravated during the study
- Chronic neurodegenerative diseases (newly diagnosed) or aggravated during the study

#### **10.4.2 Adverse event of special interest**

Adverse Events of Special Interest (AESI) are AEs (serious or non-serious) that need to be monitored, documented, and managed in a pre-specified manner described in the protocol. Please see [Section 10.4.6.2](#) and [Appendix E](#) for additional information.

#### **10.4.3 Serious adverse events waived from expedited regulatory reporting to health authorities**

Unlike most studies where the primary efficacy variable is the resolution or improvement of an existing condition, in this study efficacy outcomes include the occurrence of life-threatening events. Indeed, participants to this study are recruited precisely because they are at high risk for these life threatening events. They are therefore expected to have at least one cardiovascular efficacy endpoint during the course of the study.

In light of the above, (primary and secondary) suspected cardiovascular efficacy endpoints as specified in this protocol will not be considered as AEs and are waived from regulatory reporting to Health Authorities except if the Investigator according to his/her best medical judgment considers these events as unexpected in the context of the underlying disease condition. In that case, the Investigator will complete an AE/SAE form (in addition to eCRF efficacy endpoint page – see below) including causality assessment within 24 hours.

For this study, all suspected cardiovascular efficacy endpoints will be reported (within 24 hours) in the specific eCRF efficacy endpoint pages; the system will automatically send the notification to the Clinical Event Committee Coordination Center at DCRI. This automatic notification will occur after the Investigator has approved the eCRF screens or after a standard time interval has elapsed, whichever comes first.

Expedited reporting to Health Authorities for the following cardiovascular outcomes will be waived:

- CV death including CHD death
- All other causes of death
- Non-fatal MI
- Non-fatal stroke
- Unstable angina requiring hospitalization
- Ischemia-driven coronary revascularization procedure
- Congestive heart failure requiring hospitalization

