##### b) Cerebral Hemorrhage

Hemorrhages in the CNS are classified as stroke if they are nontraumatic, caused by a vascular event, and result in injury to the CNS. In contrast, traumatic hemorrhages will not be characterized as stroke. Subdural hematoma will not be classified as a stroke.

The diagnoses included in this section are intracerebral hemorrhage (intraparenchymal and intraventricular) and subarachnoid hemorrhage (both aneurysmal and nonaneurysmal).

Diagnoses included in this section are not part of the primary endpoint.

- Stroke caused by intracerebral hemorrhage

Rapidly developing clinical signs of neurological dysfunction (focal or global) attributable to a focal collection of blood within the brain parenchyma or ventricular system that is not caused by trauma.

- Stroke caused by subarachnoid hemorrhage

Rapidly developing signs of neurological dysfunction (focal or global) and/or headache because of bleeding into the subarachnoid space (the space between the arachnoid membrane and the pia mater of the brain or spinal cord), which is not caused by trauma.

Hemorrhages may be further classified according to location (example, supratentorial, subtentorial, intraparenchymal etc.)

- c) Stroke not otherwise specified

An episode of acute neurological dysfunction presumed to be caused by ischemia or hemorrhage, persisting  $\geq 24$  hours or until death, but without sufficient evidence to be classified as one of the above.

Strokes not otherwise specified are part of the primary endpoint.

A functional disability assessment will be performed for strokes after 3 to 6 months following the start date of the event (see [Appendix I](#)).

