## 10.5 OBLIGATIONS OF THE SPONSOR

During the course of the study, the Sponsor will report in an expedited manner all SAEs that are both unexpected and at least reasonably related to the IMP (Suspected Unexpected Serious Adverse Reaction[SUSAR]), to the Health Authorities, IECs/IRBs as appropriate and to the Investigators.

In addition, the Sponsor will report in an expedited manner all SAEs that are expected and at least reasonably related to the IMP to the Health Authorities, according to local regulations.

In this study, cardiovascular efficacy endpoints specified (primary and secondary efficacy endpoints) are waived from expedited reporting to Health Authorities providing an agreement has been reached with them.

Also some other AEs may be considered related to the underlying condition and thus will not be considered unexpected as given in the Investigator's Brochure.

Any other AE not listed as an expected event in the Investigator's Brochure or in this protocol will be considered as unexpected.

The Sponsor will report all safety observations made during the conduct of the trial in the clinical study report (CSR).

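### The expedited-reporting waiver in Protocol 10.4.3 reaches non-fatal hemorrhagic stroke, which is in no efficacy endpoint, and its bullet on other deaths is not reconciled with 10.5

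*Protocol*

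**What the plan says.** Protocol 10.4.3 sets the scope of the waiver first. In its words, "suspected cardiovascular efficacy endpoints as specified in this protocol will not be considered as AEs and are waived from regulatory reporting to Health Authorities". This holds for primary and secondary endpoints alike. There is one exception: the waiver lifts when the investigator judges that the patient's disease does not make such an event expected. An AE/SAE form with a causality assessment is then due within 24 hours, on top of the endpoint page.

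The section then gives a list, introduced by "Expedited reporting to Health Authorities for the following cardiovascular outcomes will be waived". Two of its seven entries are "All other causes of death" and "Non-fatal stroke". Neither carries a qualifier, and the list does not repeat the exception.

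Protocol 10.5 commits the sponsor to expedited reporting of "all SAEs that are both unexpected and at least reasonably related to the IMP". Its own waiver covers only the specified cardiovascular efficacy endpoints, and only where the authorities have agreed. Any other AE listed as expected in neither the Investigator's Brochure nor the protocol counts as unexpected.

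On hemorrhagic stroke, Protocol 9.1.6.3 states: "Diagnoses included in this section are not part of the primary endpoint".

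**The concern.** A reporting waiver in an outcome trial has a clear purpose: events already counted and adjudicated as endpoints need not also be sent, and unblinded, one at a time. That reasoning covers endpoints only. If the list is broader than the endpoints, an event can fall between the two systems, neither an endpoint for analysis nor an adverse event with a recorded causality judgment.

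Non-fatal hemorrhagic stroke is in that position. Protocol 10.6.3 says the lower limit of safe LDL-C lowering is not yet established, so it matters that an individual case can be recognized as a suspected reaction while the trial is running. What is at stake is the single-case route: whether causality is recorded at the time, and whether the sponsor has what it needs to apply 10.5.

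**Working it through.** No arithmetic applies. The check sets the waiver list against the endpoint definitions and then follows the two doubtful entries through the reporting rules.

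**Step 1: each list entry against Protocol 9.1.1, 9.1.3 and 9.1.4.**

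| Entry in 10.4.3 | Matching efficacy endpoint | Within a waiver for cardiovascular efficacy endpoints? |
|---|---|---|
| CV death, including CHD death | Primary (CHD death); main secondary, any CV event (CV death) | Yes |
| All remaining deaths | Main secondary, all-cause mortality | An efficacy endpoint, but not a cardiovascular one |
| Non-fatal MI | Primary | Yes |
| Non-fatal stroke, any type | Ischemic or not otherwise specified only | Only in part |
| Hospitalized unstable angina | Primary | Yes |
| Ischemia-driven revascularization | Main secondary, any CHD event; other secondary | Yes |
| Hospitalized heart failure | Other secondary | Yes |

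Five entries fit. Two do not.

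**Step 2: non-fatal hemorrhagic stroke.** Wherever non-fatal stroke enters an endpoint, it is ischemic, and 9.1.1 and 9.1.6.3 add stroke not otherwise specified. Cerebral hemorrhage is excluded from the primary endpoint, and no secondary endpoint takes in the non-fatal form.

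An event reported on an endpoint form and finally diagnosed by the investigator as hemorrhagic stroke is among those that SAP 3.4.6 describes separately, because they are not reported as adverse events. Under 10.4.3 the form that carries causality is required only if the investigator finds the event unexpected for the underlying disease. That gives two paths:

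- Judged unexpected for the disease: AE/SAE form with causality within 24 hours, and 10.5 can be applied.
- Judged in keeping with the disease: endpoint page only, no causality assessment, and the related-and-unexpected test of 10.5 has nothing to work on.

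The first test looks at the patient's disease. The second looks at the product's reference documents. They can disagree, and the first decides whether the second is ever reached.

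**Step 3: other deaths.** CV deaths have their own entry, so the residual entry means non-cardiovascular and undetermined deaths. Undetermined deaths count as CHD death under 9.1.1. The remainder are non-cardiovascular deaths, which all-cause mortality covers but which are not cardiovascular outcomes. For one that is related to IMP and unexpected, 10.5 requires an expedited report while the 10.4.3 list, read by itself, waives it. The waiver in 10.5 does not resolve this, because it too is limited to cardiovascular efficacy endpoints.

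**The case against.** The case on the other side is substantial, and much of it stands.

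- *All deaths are endpoints.* All-cause mortality is a main secondary endpoint and every death goes to the CEC (Protocol 9.1), so the entry on other deaths corresponds to something the trial counts. This stands. It makes outright deletion of that entry a debatable trade-off, since Protocol 8.3.6 allows sponsor unblinding for some related, unexpected SAEs.
- *The exception works where it matters most.* A fatal non-cardiovascular drug reaction is hard to call expected in coronary disease, so the 24-hour form would usually be triggered, and 10.5 applies separately. This stands for deaths. It is weaker for hemorrhagic stroke, which an investigator might see as part of vascular disease. Protocol 10.5 itself allows some events to be attributed to the underlying condition, but by reference to the Investigator's Brochure.
- *Oversight does not depend on single-case reports.* SAP 3.4.6 tabulates hemorrhagic strokes by treatment group, per investigator and per CEC, and the CV DMC reviews unblinded safety data that include cardiovascular outcomes, adjudicated or not (Protocol 6.4). This stands, but group counts do not record causality case by case.
- *Appendix E may settle it.* The appendix summarizing site reporting is not in the text available for review, so nothing is counted against the plan for its absence. Section 10.4.3 would still have to agree with it.

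A reader might infer that fatal events drop out of the death tables. The documents do not support that: SAP 3.4.5.2 tabulates deaths from first injection to the common study end date by CEC-adjudicated cause, independently of the AE page. A reader might also infer that fatal hemorrhagic strokes lie outside the endpoints. They do not: Protocol 9.1.7.1 treats death from intracerebral hemorrhage as CV death, which enters the any-CV-event endpoint.

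**Conclusion.** The list in 10.4.3 is wider than the section's own scope and than the waiver in 10.5. The clear defect is the unqualified stroke entry: it takes in non-fatal hemorrhagic stroke, and SAP 3.4.6 shows that such events on endpoint forms carry no AE record. The entry on other deaths is a lesser matter of labelling and reconciliation, because these deaths are counted as endpoints and the exception and 10.5 both point toward reporting the ones that matter.

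The size is small. Only non-fatal hemorrhagic strokes, and non-cardiovascular deaths that are both related and unexpected, are touched. The documents give no rate for either, so no count is offered; few cases are to be expected. No endpoint, test or error rate is affected. The conclusion rests on reading the list as worded and assumes that Appendix E does not already narrow it.

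**What to change.** 1. In the 10.4.3 list, replace the stroke entry with 'Non-fatal ischemic stroke (including stroke not otherwise specified)'.
2. State that a non-fatal stroke diagnosed as hemorrhagic is recorded as an SAE with a causality assessment and is still sent to the CEC.
3. Keep the entry on other deaths if the sponsor wishes, but reconcile it with 10.5: add that a non-cardiovascular death that is related to IMP and unexpected under 10.5 is still reported in an expedited manner.
4. Align Appendix E and SAP 3.4.6 with the result.

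The cost is amendment wording, a reminder to sites, and a few extra SAE forms and expedited reports, with sponsor-side unblinding of those cases. No endpoint data are lost, because submission to the CEC is unchanged.
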